7.1.9 Mean Daily Glucose and Mean Post-prandial Glucose (Self-monitored)

All subjects will perform a 6 Point SMBG profile for any 3 days (to be included in the calculation of mean daily glucose, the measurements do not need to be recorded over 3 consecutive days, nor do they need to have 3 complete days of measurements.). These are scheduled between Week (-2) to Week (-1), Week 11-12, Week 23-24 and Week 51-52. Blood glucose readings will consist of 3 pre-prandial measurements and 3 post-prandial measurements. Meals are considered to be breakfast, lunch and dinner. A minimum of 2 days of all 6-point SMBGs are required to complete the 6-point SMBG profile for each period. Similarly a minimum of 2 days of all post prandial SMBGs will be required for summary of postprandial averages. The pre-prandial and postprandial measurements collected at the nominal time points will be considered for analysis.

Glucose concentrations at each of the 6 time points will be averaged over the 3 days to derive the mean glucose concentrations at each of the 6 time points. The mean daily glucose (MDG) will then be calculated as the average over the average glucose concentrations at the 6 time points. Only complete pairs of the average preprandial and postprandial blood glucose values will be used for the calculation. For example, if the available average time point data for a subject at a visit are

pre-breakfast, post-breakfast, and pre-dinner, then the daily average will be calculated as (pre-breakfast + post-breakfast)/2. The average value for pre-dinner is excluded for the calculation since the average value for the post-dinner is missing. The mean post-prandial glucose will be calculated as the average over the average glucose concentrations at the 3 post-prandial time points.

7.1.10 Mean Amplitude of Glucose Excursions (MAGE) of continuous glucose monitoring system readings

Mean amplitude of glucose excursions (MAGE) is calculated using data from continuous glucose monitoring (CGM). MAGE for a 24-hour period equals “the arithmetic mean of the blood glucose increases or decreases (from blood glucose nadirs to peaks or vice versa) when both ascending and descending segments exceeded the value of one standard deviation of the blood glucose for the same 24-hour period”¹. Therefore, it corresponds to the mean of absolute differences between consecutive maxima and minima, as long as these differences are greater than one standard deviation for the same 24-hour period.

Here an example of calculation as described in the original publication of MAGE in ³.

Figure 7.1.10-1: Blood glucose curve of a subject studied on intermediate-acting insulin regimen.

[figure not shown]

Figure from Service, et al., 1970 ³

As stated in ³, the calculation of MAGE for subject in Figure 7.1.3-1 “is as follows: the first excursion, 333 to 208 mg./100 mL, is 125 mg./100 mL, exceeding the value of one standard deviation; 62. The first blood glucose increase, from 208 to 322 mg./100 mL, is 114 mg/100 ml [...] and also exceeds one standard deviation; however, the subsequent blood glucose decrease of 35 mg./100 mL (from 322 to 287 mg./100 mL) is less than one standard deviation and so this excursion is not counted. The next blood glucose increase, from 208 to 432 (224 mg./100 mL), and decrease, from 432 to 137 mg./100 mL (295 mg./100 mL), both exceed the value of one standard deviation; therefore this glycemic excursion is 295 because the first excursion is in a peak-to-nadir direction and the direction of calculation (peak-to-nadir or nadir-to-peak) is established, for that CBGA, by the direction of the first excursion.” Continuing, the next peak is 272 mg./100 mL which corresponds to an excursion of 135 mg./100 mL. The next excursion is 116 mg./100 mL to a nadir at 156 mg./100 mL, followed by an excursion of 160 mg./100 mL to a peak at 316 mg./100 mL. The next nadir is at 173 mg./100 mL corresponding to an excursion of 143 mg./100 mL and it is followed by a peak at 322 mg./100 mL and a respective excursion of 149 mg./100 mL and by a nadir at 196 mg./100 mL and a respective excursion of 126 mg./100 mL. The next excursion is 178 mg./100 mL to a peak at 374 mg./100 mL, followed by one of 332 mg./100 mL to a nadir at 42 mg./100 mL and one of 186 mg./100 mL to the subsequent peak of 228 mg./100 mL. Finally the last couple of excursions are 149 mg./100 mL to the next nadir at 79 mg./100 mL and 163 mg./100 mL to the final peak point at 242 mg./100 mL. Therefore, MAGE for this subject profile corresponds to the arithmetic mean of all excursions and equals approximately 177 mg./100 mL.

Note although the above example refers to glucose expressed in mg/dL, calculation of MAGE with glucose readings expressed in standard international units (i.e. mmol/L) will follow the same principle.

For calculating MAGE the following definitions apply:

- **Segment:** the ascending or descending part between a nadir and a peak.
- **Qualifying excursion:** A change from nadir to peak (or from peak to nadir) where both the excursion and the following segment in the opposite direction exceed 1 standard deviation for the whole 24 hour period for the subject.

MAGE is calculated as the arithmetic mean of all qualifying excursions during the 24 hours.

Phase V® is collecting the data and performing the analyses for CGM in this study. More details on the collection and analysis is provided in Appendix 1.

7.2 Study Conduct

Subjects who deviate from protocol conditions (e.g., important inclusion/exclusion criteria) will be reported as having significant protocol deviations. Significant protocol deviations that are determined to affect the primary efficacy results are deemed Relevant Protocol Deviations (RPDs). A list of relevant protocol deviation criteria, along with the consequent handling of data should those deviations occur, is given in Table 1. There will be no data exclusion for significant protocol deviations only.

Table 7.2-1: List of Relevant Protocol Deviations

RPD #	RPD Criteria	Exclusion Type	Exclusion Level
1	Randomized subjects without type 2 diabetes or with central laboratory HbA1c more than 0.2% outside of specified limits of $\geq 8.0\%$ and $\leq 12\%$	Complete	This will be assessed using the screening value or at an unscheduled visit prior to randomization.
2	Randomized subjects who did not receive stable dose of metformin with or without a stable dose of SU	Complete	Subjects not taking ≥ 1500 mg metformin for at least 8 weeks prior to enrollment
3	Randomized subjects with abnormal TSH and free T4 missing or abnormal at enrollment or at an unscheduled visit prior to randomization	Complete	Because the T4 test is collected reactively to TSH, this deviation would only occur if there were an abnormal TSH and free T4 value
4	Randomized subjects with history of hemoglobinopathy, (with the exception of sickle cell trait (SA) or thalassemia minor), and/or chronic or recurrent hemolysis.	Complete	
5	Randomized subjects who used antihyperglycemic medication (other than protocol required medications) for 14 or more consecutive days during the short-term open-label treatment period.	Partial /Complete	Exclusion will start from the 14th consecutive day that the medication was taken/ Subjects who were on treatment < 14 days and used prohibited antihyperglycemic medication will be excluded
6	Randomized subjects that were treated with any systemic corticosteroid therapy for ≥ 5 consecutive days initiated during the short-term open-label treatment period.	Partial /Complete	Exclusion will start from the 5th day that the medication was taken. Subjects who were on treatment < 5 days and used prohibited corticosteroid medication will be excluded
7	a. Randomized subjects who took no dose of metformin or dose of metformin outside dose range for ≥ 2 consecutive weeks in the short-term open-label treatment period b. Randomized subjects who were on stable dose of SU at baseline but took no dose of SU or different SU dose for ≥ 2 consecutive weeks in the short-term open-label treatment period	Partial /Complete	Exclusion will start from the 14th consecutive day that metformin was either not taken or outside range of ≥ 1500 or dose of SU was changed for subjects who were taking SU. Subjects who were on treatment < 14 days and did not take metformin/SU according to protocol will be excluded
8	Randomized subjects who receive no study medication (saxagliptin, dapagliflozin, or insulin glargine) for ≥ 2 consecutive weeks in the short-term open-label treatment period	Partial /Complete	Exclusion will start from the 14th consecutive day that the medication was not taken in an interruption. Subjects who were on treatment < 14 days and did not receive study medication (saxagliptin,

Table 7.2-1: List of Relevant Protocol Deviations

RPD #	RPD Criteria	Exclusion Type	Exclusion Level
9	Randomized subjects who received incorrect study medication (saxagliptin, dapagliflozin, or insulin glargine) or dosing for ≥ 2 consecutive weeks in the short-term open-label treatment period	Partial/Complete	dapagliflozin, or insulin glargine) will be excluded Exclusion will start from the 14th consecutive day that the incorrect medication was taken. Subjects who were on treatment < 14 days and did not receive correct study medication (saxagliptin, dapagliflozin, or insulin glargine) or dosing will be excluded
10	Randomized subjects who are judged to be noncompliant in terms of overall compliance, i.e., who took less than 80% or more than 120% of their prescribed dose of study medication during the short-term open-label treatment period.	Complete	

* If a patient has an unacceptable/missing value at screening visit but then has an unscheduled visit prior to randomization with an acceptable value, the patient will not be considered an RPD.

7.3 Study Population

7.3.1 Subject Disposition

The disposition of subjects for the screening period, lead-in period, and the 24-week short-term treatment period will be summarized. The summary of status in the screening period will include all subjects in Enrolled Subjects Data Set. Reasons for discontinuation for subjects who discontinued from the lead-in period and from the short-term treatment period will be tabulated and listed. The summary will be presented by randomized treatment group and overall.

The summary of status in the combined short-term plus long-term treatment periods will include all subjects in Randomized Subjects Data Set and be presented by randomized treatment group. This summary will include subjects entering, completing and discontinuing the long-term treatment period with reasons for discontinuation.

7.3.2 Demography and Other Baseline Characteristics

Demographic and other baseline characteristics, including diabetes-related characteristics and renal function characteristics will be summarized overall and by treatment group (where applicable) using the Randomized Subjects Data Set and/or the Evaluable Subjects Data Set. Demographic and common baseline characteristics are listed in Table 7.3.2A. Common diabetes related baseline characteristics are listed in Table 7.3.2B. Common renal function baseline characteristics are listed in Table 7.3.2C.

Table 7.3.2A: Demographic and Common Baseline Characteristics

Characteristic	Summarized as	Categories
Gender	Categorical	Male, Female
Age	Categorical and Continuous	< 65 yrs ≥ 65yrs ≥65yryrs
Female Age	Categorical	≤ 50 yrs > 50 yrs
Race	Categorical	White, Black or African American, Asian, Other
Ethnicity	Categorical	Hispanic/Latino, Non Hispanic/Latino
Body Weight	Continuous	-
Height	Continuous	
Body Mass Index	Categorical and Continuous	< 25 kg/m ² ≥ 25 kg/m ² ≥ 27 kg/m ² ≥ 30 kg/m ²
Geographic Region	Categorical	As defined in Appendix 4

Table 7.3.2B: Common Diabetes-Related Baseline Characteristics

Characteristic	Summarized as	Categories
Duration of Type 2 Diabetes	Categorical and Continuous	< 3 yrs ≥ 3 and ≤ 10 yrs > 10 yrs
HbA1c	Categorical and Continuous	<8% ≥ 8 and < 9% ≥ 9%
FPG	Continuous	-

Table 7.3.2C: Common Renal Function Baseline Characteristics

Characteristic	Summarized as	Categories
eGFR (MDRD)	Categorical and Continuous	<60 mL/min/1.73m ² ≥60-<90 mL/min/1.73m ² ≥ 90 mL/min/1.73m ²

All summaries of continuous characteristics will be based on non-missing observations. For categorical characteristics, percentages will be calculated out of the total number of subjects in the data set, overall and by treatment group, where applicable (i.e., each denominator includes the number of subjects with missing/unknown values for the characteristic).

7.3.3 Specific and General Disease History

The number (percent) of subjects with diabetes, diabetes-related disease histories will be summarized by treatment group and overall using the Randomized Subjects Data Set for the short-term treatment period.

The number (percent) of subjects with general medical history findings will also be summarized by treatment group and overall using the Randomized Subjects Data Set for the short-term treatment period.

7.4 Extent of Exposure

7.4.1 Study and Rescue Medication

The extent of exposure to study medication during the 24-week short-term open-label treatment period is defined as the difference between the last and the first dose of study medication of the short-term open-label treatment period plus 1 day. The extent of exposure to study medication will be summarized using the Treated Subjects data set for the short-term open-label treatment period and the short-term open-label treatment period prior to rescue, where the number and percent of subjects with an extent of exposure within specified day ranges (1-6, 7-14, 15-28, 29-42, 43-56, 57-70, 71-84, 85-168, 169-182, \geq 183 days) will be presented by treatment group. The mean (SD), median and range of the number of days of exposure will also be presented. Summaries will be presented excluding and including periods of interruptions (defined by record of 0 tablets of study medications on the case report form (CRF)). Total daily insulin dose at Week 12 and Week 24 during the 24-week open-label treatment period will be summarized for the subjects taking Insulin. All rescue medication use during the 24-week short-term open-label treatment period will be summarized and listed by treatment group.

The extent of exposure to study medication during the combined ST+LT treatment periods is defined as the difference between the last dose of ST or LT treatment and the first dose of study medication plus 1 day. The extent of exposure to study medication will be summarized using the Treated Subjects data set for the combined ST+LT treatment periods, regardless of and prior to rescue. The number and percent of subjects with an extent of exposure within pre-specified day ranges (1-90, 91-180, 181-270, and $>$ 270 days) will be presented by treatment group. The mean (SD), median and range of the number of days of exposure will also be presented. Summaries will be presented including periods of interruptions (defined by record of 0 tablets of study medications on the case report form (CRF)). All rescue medication use during the combined ST+LT treatment periods will be summarized and listed by treatment group.

A listing of subjects by batch number of study medication will also be generated for both ST and ST+LT treatment periods.

7.4.2 Concomitant Medications

Concomitant medications for the short-term treatment period will be any medication taken from start of the short-term treatment period up to the end of the short-term treatment period.

Concomitant medications for combined short-term plus long-term treatment periods will be any medication taken from start of the ST treatment period up to the end of the combined ST+LT treatment periods.

Concomitant medications for both the ST and ST+LT will be summarized using the Treated Subjects dataset by drug class and (generic) drug name. A summary table by drug class and generic drug name will be generated for each of the following:

- all concomitant medication
- all concomitant diuretic medication

- all concomitant ARB and/or ACE-I medication
- all concomitant anti-hypertensive medication

In addition, a listing of all non-study medications taken during the study (including prior and concomitant) will be produced.

Missing and partial date handling of start and stop dates of concomitant medications is described in Section 8.7. The WHO dictionary will be used to code the non-study medication.

7.4.3 Measurements of Treatment Compliance

Percent treatment compliance will be calculated for ST and ST+LT treatment period for each treatment group. For each subject, percent compliance for saxagliptin plus dapagliflozin treatment group is defined as the total number of tablets taken divided by the total number of tablets that should have been taken, multiplied by 100. Percent compliance for Insulin treatment group is calculated as number of days insulin dose was taken divided by the number of days insulin dose should have been taken (duration of exposure), multiplied by 100. A subject is considered compliant if percent compliance is $\geq 80\%$ and $\leq 120\%$. The number and percent of subjects considered compliant will be summarized for each treatment group using the Treated Subjects data set.

For the Short-term:

The number of tablets that should have been taken is calculated as 1 + the number of days from the first short-term treatment period dose recorded in the “Record of Study Medication” to the last short-term treatment dose, times the prescribed daily dose (i.e. 2 tablets per day, one from each bottle). The number of tablets taken is the total number of tablets recorded (sum of bottle 1 and bottle 2) as taken based on the CRF, summed over the days counted when calculating the number of tablets that should have been taken, including the day of the last short-term treatment dose.

For the combined ST and LT:

The number of tablets that should have been taken is calculated as 1 + the number of days from the first treatment period dose recorded in the “Record of Study Medication” to the last treatment dose, times the prescribed daily dose (ie, 2 tablets per day, one from each bottle). The number of tablets taken is the total number of tablets recorded (sum of bottle 1 and bottle 2) as taken based on the CRF, summed over the days counted when calculating the number of tablets that should have been taken, including the day of the last treatment dose.

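### Tablet compliance is computed on both bottles pooled, so a subject with scattered misses who takes as little as 60% of one drug can count as compliant with the combination and pass RPD 10

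*SAP*

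**What the plan says.** SAP section 7.4.3 defines compliance in the saxagliptin plus dapagliflozin arm by a single ratio, "defined as the total number of tablets taken divided by the total number of tablets that should have been taken, multiplied by 100". Both parts of the ratio pool the two drugs:

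- **Numerator:** "The number of tablets taken is the total number of tablets recorded (sum of bottle 1 and bottle 2"), as recorded on the CRF.
- **Denominator:** the days from first to last short-term dose, inclusive, "times the prescribed daily dose (i.e. 2 tablets per day, one from each bottle").

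A subject is compliant if the result lies from 80% to 120% inclusive. Section 8.9 only refers back to 7.4.3, and no threshold for a single bottle appears anywhere in the SAP.

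The same limits decide who stays in the per-protocol population. RPD 10 in Table 7.2-1 (section 7.2) covers "Randomized subjects who are judged to be noncompliant in terms of overall compliance", meaning those who "took less than 80% or more than 120% of their prescribed dose of study medication" in the short-term period, and the exclusion is complete.

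Two other entries in that table name the drugs individually. RPD 8 concerns "Randomized subjects who receive no study medication (saxagliptin, dapagliflozin, or insulin glargine) for ≥ 2 consecutive weeks". RPD 9 concerns incorrect study medication or dosing over the same minimum duration. Both normally remove data only from the 14th consecutive day; complete exclusion is for subjects on treatment for less than 14 days.

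**The concern.** The trial's question is about two drugs given together (sections 1 and 3.1). A compliance measure that adds the tablets cannot tell a subject who took 80% of each drug from one who took all of one and 60% of the other. Full use or over-use of one drug hides under-use of its partner.

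Two outputs inherit this. The compliance table in section 7.4.3 would report such subjects as compliant with the combination. The Evaluable Subjects Data Set (section 6.3.5) would not lose them through RPD 10. That set is used to repeat the primary non-inferiority analysis (section 7.5.2) and the two secondary non-inferiority analyses (section 7.5.4). What is at stake is how clearly those supportive results can be read as results in subjects who took both drugs.

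**Working it through.** The SAP gives no worked compliance figure, so there is none to reproduce. The check applies its definition directly.

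**Inputs.** One tablet from each bottle per day, and a band of 80–120% inclusive (section 7.4.3). Duration D of 168 to 170 days is an assumption: 24 weeks × 7 = 168, and the Week 24 target day in Table 8.4-1 is 169. The percentages do not depend on D apart from rounding to whole tablets.

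**Formula.** Let T1 and T2 be the tablets taken from each bottle, with P1 = 100 × T1/D and P2 = 100 × T2/D. Then

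pooled compliance = 100 × (T1 + T2)/(2D) = (P1 + P2)/2.

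The lower limit therefore requires only P1 + P2 ≥ 160, that is, P2 ≥ 160 − P1.

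| One bottle | Other bottle | Pooled | Pooled rule | Each bottle within 80–120%? |
|---|---|---|---|---|
| 100% | 60% | 80% | compliant | no |
| 100% | 59% | 79.5% | non-compliant | no |
| 100% | 50% | 75% | non-compliant | no |
| 100% | 0% | 50% | non-compliant | no |
| 95% | 65% | 80% | compliant | no |
| 95% | 60% | 77.5% | non-compliant | no |
| 90% | 70% | 80% | compliant | no |
| 120% | 40% | 80% | compliant | no |
| 150% | 50% | 100% | compliant | no |

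So 60% is the exact floor when the other bottle is taken at 100%. A lower value passes only if the other drug is over-used. In the last row both drugs lie outside the SAP's own band, yet the score is 100%.

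**In whole tablets.**

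- D = 170: 170 + 102 = 272 of 340 due = 80.0%, with 170 − 102 = 68 tablets of one drug missed.
- D = 168: the smallest passing count for the second bottle is 101 (60.1%), since 168 + 101 = 269 of 336 = 80.06%, with 67 tablets missed.

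**Would RPD 8 or RPD 9 catch this subject?** Not if the misses are scattered. Missing one drug on two days of every five gives 102 of 170 tablets (60%), and the two days can be placed so that the longest gap is one day. Neither rule's two-week condition is met. If the misses form a run of 14 days or more, either rule may apply. RPD 8 does not make clear whether missing one of the two drugs counts as receiving no study medication.

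**The case against.** The strongest reply is that the rule is explicit and consistent: RPD 10 speaks of overall compliance and section 7.4.3 defines an overall figure. Section 6.3.5 describes relevant deviations as those that could affect interpretability; it does not say that every retained subject took both drugs as prescribed. On this view a per-bottle rule is a preference, and no contradiction has been shown. That is fair. The point is a weakness in the measure, and the two sections do agree with each other.

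A reader might also infer three stronger things, none of which the SAP supports:

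- **That a subject taking one drug in full and about half of the other is retained.** That subject scores 75% and is completely excluded.
- **That an affected subject always stays in the evaluable set.** A sustained gap, or sustained wrong dosing such as over-use of one bottle, may fall under RPD 8 or RPD 9 and remove later data, possibly including Week 24.
- **That the non-inferiority claim is at risk.** The primary analysis and all hierarchical tests use the Randomized Subjects Data Set, and section 7.5.1 keeps the evaluable-set analyses out of the hierarchy. Under-use of a component would be expected to weaken HbA1c lowering in the saxagliptin plus dapagliflozin arm. That makes an upper confidence limit below 0.3% harder to reach. Only the over-use patterns have an unclear direction.

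Finally, nothing in the SAP suggests that the two bottles will often diverge, and a per-bottle rule is stricter in one arm only, because insulin compliance is a single days-taken percentage. Both remarks stand. They limit the size of the point and shape the fix.

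**Conclusion.** The point holds within limits. The pooled calculation counts as compliant, and RPD 10 does not exclude, a subject who takes 100% of one drug and as little as 60% of the other, or less if the first is over-used. It rests on two conditions: the other bottle is taken at essentially 100% or more when the shortfall is as deep as 60%, and the misses do not form a run of two weeks or longer. The direction given for under-use assumes that missing one component reduces the glycemic effect.

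The effect is confined to the compliance table and the supportive evaluable-set analyses. The number of subjects cannot be estimated from the SAP. This is a cheap improvement in interpretability, and the primary conclusion does not depend on it.

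**What to change.** In section 7.4.3, compute and report percent compliance separately for each bottle. For the compliance table and RPD 10, treat a saxagliptin plus dapagliflozin subject as compliant only if both percentages lie within the SAP's existing 80–120% band. This adds no new threshold and matches RPD 8 and RPD 9, which already list the drugs individually. Report how many subjects change status against the pooled rule.

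The cost is a few lines of SAP text and programming, settled before evaluable-set exclusions are decided. Section 7.4.3 sums two bottle counts from the CRF, so the data appear to be available already. The downside is that a few more subjects may be excluded after randomization, in the saxagliptin plus dapagliflozin arm only. For that reason the evaluable-set results should also be shown under the pooled rule, so that any difference between the two can be seen.
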